8 STUDY DESIGN

8.1 Overall Study Design

This is a Phase 3b, multicenter, double-blind, parallel group, randomized extension study that will evaluate the efficacy and safety of 2 treatment regimens of edaravone for an additional period of up to 48 weeks following Study MT-1186-A02 in subjects with ALS as follows:

- Group 1: Oral edaravone 105 mg dose once daily in each 28-day cycle for up to 48 weeks or until the drug is commercially available in that country.
- Group 2: Oral edaravone 105 mg dose for 10 days followed by 18-day placebo (regimen denoted as on/off) in each 28-day cycle for up to 48 weeks or until the drug is commercially available in that country.

Subjects who meet study MT-1186-A04 eligibility criteria, will continue in the same treatment group/regimen that they were in during Study MT-1186-A02.

A schedule of assessment of all study procedures is provided in Table 1.

The Week 48 study procedures from Study MT-1186-A02 will be used as the screening/entry criteria for Study MT-1186-A04, followed by a treatment period of up to an additional 48 weeks or until oral edaravone is commercially available in each country, whichever time period is shorter, and a safety follow-up period of 2 weeks.

During the conduct of Study MT-1186-A04, the dose of edaravone may be adjusted or the study may be stopped based on the interim futility or final analyses performed for Study MT-1186-A02, taking into consideration the benefit and risk balance. However, unless any significant safety issue is found based on these 2 analyses, the same regimen will be kept while maintaining the blind conditions for all site-facing personnel and all personnel directly involved with the conduct of the study.

Concomitant use of riluzole is permitted throughout the course of the study when the dose and regimen remain unchanged from the screening visit evaluation of ALSFRS-R of Study MT-1186-A02 through the end-of-treatment (EOT) or early termination (ET) of Study MT-1186-A04. Dose reduction, dose interruption, or discontinuation due to the onset of AEs, progression of dysphagia, or gastrostomy while on oral edaravone 105 mg are allowed. The use of AMX0035 will be allowed for patients in the event that it becomes commercially available via prescription in their respective country. AMX0035 should be taken at least 1 hour after MT-1186/oral edaravone dosing.

EOT assessments will occur at Week 48 (Visit 5).

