8.3.1.2. Demographic and Other Baseline Characteristics

8.3.1.2.1. Demographics:

This data not collected in MT-1186-A04 will be taken from MT-1186-A02.

Continuous: age, height, weight, Body Mass Index (BMI);

Categorical: age categorized as \leq 64 years versus \geq 65 years, and \leq 19, 20–29, 30–39, 40–49,

Mitsubishi Tanabe Pharma America, Inc.

50–59, 60–69, ≥ 70, gender, race, ethnicity, country and region defined as America- AM, Europe -EU and Asia Pacific - AP

O BMI will be calculated as weight at screening (kg) / {height at screening (m)}² and reported to 1dp.

Table 2: Demographic and Baseline Characteristics

Category	Item	Type of Data	Definition/Breakdown
	Gender	Binary	Male, Female
	Race	Categorized	 White Black or African American Asian – Japanese Asian - Not Japanese American Indian or Alaska Native Native Hawaiian or Pacific Islander Not Reported Other
Demography		Continuous	
	Age (year)	Categorized	\leq 19, 20–29, 30–39, 40–49, 50–59, 60–69, \geq 70
		Categorized (binary)	<65, ≥ 65
	Height (cm)	Continuous	
	Body weight (kg)	Continuous	
	BMI	Continuous	Weight at screening (kg) / {height at screening (m)} ²
	Country	Categorized	United States, Canada, Germany,
			Italy, Switzerland, Japan, South
			Korea
	Region	Categorized	1. America-AM
	•		2. Europe -EU
			3. Asia Pacific - AP
	Ethnicity	Categorized	1. Hispanic or Latino
			2. Not Hispanic or Latino
			3. Not Reported
			4. Unknown

Mitsubishi Tanabe Pharma America, Inc.

8.3.1.2.2. ALS History:

This data not collected in MT-1186-A04 will be taken from MT-1186-A02.

Continuous:

- (1) Disease Duration from Onset of Symptoms (years) and from ALS Diagnosis (years),
- (2) ALSFRS-R score at screening,
- (3) ALSFRS-R at Baseline,

Categorical:

- (1) ALSFRS-R Deterioration Rate of (-1,-2) or (-3,-4),
- (2) Disease duration from Onset of Symptoms categorized at <1 year vs ≥ 1 year and from Onset of ALS Diagnosis categorized at <1 year vs ≥ 1 year,
- (3) Initial symptom categorized as 'Bulbar onset' or 'Limb onset',
- (4) ALS Diagnosis categorized 'Sporadic' or 'Familial',
- (5) Categorical El Escorial revised Diagnostic,
- (6) Concomitant use of riluzole 'Present' or 'Absent',
- (7) Previous use of AMX0035 'Present' or 'Absent',
- (8) Concomitant use of AMX0035 'Present' or 'Absent',

Table 3: ALS History Parameters

Category	Item	Type of Data	Definition/Breakdown
	Disease duration from Onset of	Continuous	(Date of Screening - Date of Onset of Symptoms*)/365.25

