8.3.1.3. Concomitant Medication

Definition of concomitant medications in the protocol

Concomitant medication is defined as any medication, other than the study drug, which is taken after the first dose administration in Study MT-1186-A02, including prescription, herbal and over-the-counter medications. All concomitant medications taken while the subject is participating in the study will be recorded in the eCRF. All medications will be classified using the Anatomical Therapeutic Chemical (ATC) classification codes and preferred drug names from the World Health Organization Drug Dictionary (WHO-DD, version from September 2019).

Concomitant medications, except for riluzole, will be summarized by ATC level 2 categories and preferred name. Riluzole administration will be summarized separately.

Rules to determine concomitant medications

Medications with a stop date before the first date of study drug dosing in MT-1186-A02 will be considered prior medications. Medications with start date or stop date on or after the first date of study drug dosing in MT-1186-A02 or ongoing up to week 48 in MT-1186-A04 will be considered concomitant medications.

If the medication start date is incomplete, then it will be imputed as follows for the purpose of determining concomitant use:

• If the start date is completely missing, the start date will be equal to the first dose date.

However, if the stop date is not missing and is before the first dose date, then the stop date will be used instead.

Mitsubishi Tanabe Pharma America, Inc.

- If the start day is missing, the first day of the month will be used.
- If the start day and month are missing, then the first day of the first month (January) will be used.

If the medication stop date is partial, then it will be imputed as follows for the purpose of determining concomitant use:

- If the stop date is completely missing and the medication is not ongoing, the stop date will be equal to the last dose date or date of completion/withdrawal, whichever is the latest.
- If the stop day is missing, the last day of the month will be used.
- If the stop day and month are missing, then the last day of the last month (December) will be used.

Integration of continued concomitant medications from MT-1186-A02 to MT-1186-A04:

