9.1.4. Intercurrent Events (ICEs) Distribution

ICEs distribution will be summarized by treatment group using descriptive statistics for the Randomized set:

- The number (%) of subjects with ICE1 of Additional/new AMX0035 treatment occurred during MT-1186-A02 and MT-1186-A04
- The number (%) of subjects with ICE2 of Death event occurred during MT-1186-A02 and MT-1186-A04

Mitsubishi Tanabe Pharma America, Inc.

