9.4. Subgroup analysis

The following subgroups will be analyzed for the time to at least 12-point decrease in ALSFRS-R or death (the primary endpoint) and time to death, tracheostomy, or permanent assisted mechanical ventilation endpoints (the secondary endpoint). For the time to event endpoints, the same Cox proportional hazard regression model will be used while adding the subgroup variable as well as the subgroup by treatment interactions. The influence of each subgroup factor will be investigated using the p-values for the interaction terms. The subgroup analysis will be performed on the Randomized set. In addition, forest plot depicting the treatment effect and 95% CI for all subgroups will be displayed for the time to at least 12-point decrease in ALSFRS-R or death and the time to death, tracheostomy, or permanent assisted mechanical ventilation.

Note: In some subgroup analyses, some factors will be statistically adjusted (e.g., in the country subgroup analysis, the Region factor will be removed).

- Race (White; Black; Asian; Other)
- Age (>=65 years old; <65 years old)
- Region (North America; Europe; Asia)
- Body Weight at baseline in MT-1186-A02 (>=Median; <Median)
- BMI at baseline in MT-1186-A02 (>=Median; <Median)
- Country (United States; Canada; Germany; Italy; Switzerland; Japan; South Korea)
- Disease duration from onset of symptoms (<1 year; >=1 year)
- ALSFRS-R score at baseline in MT-1186-A02 (>=Median, <Median)
- ALSFRS deterioration strata for randomization (-1, -2; -3, -4)
- Initial symptom (Bulbar; Limb)
- El Escorial revised Airlie House Diagnostic Criteria (Definite ALS; Probable ALS)
- Concomitant use of riluzole (Present; Absent)
- Concomitant use of AMX0035 (Present; Absent)
- %FVC at baseline in MT-1186-A02 (>=80%, <80%)
- %SVC at baseline in MT-1186-A02 (>=80%, <80%)

Mitsubishi Tanabe Pharma America, Inc.

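### The AMX0035 Present/Absent subgroup in SAP 9.4 is largely set after randomisation, yet it enters the Cox model as a fixed factor

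*SAP*

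**What the plan says.** SAP 9.4 names fifteen subgroup factors for two time-to-event endpoints, the primary and time to death, tracheostomy or permanent assisted ventilation. One is "Concomitant use of AMX0035 (Present; Absent". For every factor, "the same Cox proportional hazard regression model will be used while adding the subgroup variable as well as the subgroup by treatment interactions". The outputs are interaction p-values ("The influence of each subgroup factor will be investigated using the p-values for the interaction terms") and a forest plot of the treatment effect by subgroup, on the Randomized set. No time-dependent term, landmark or restriction to baseline use is stated for AMX0035. Body weight, BMI, ALSFRS-R, %FVC and %SVC in the same list are each tied to A02 baseline.

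Four other places fix what the factor means:

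- SAP 8.3.1.3: "Concomitant medication is defined as any medication, other than the study drug, which is taken after the first dose administration in Study MT-1186-A02". Its date rule also counts "Medications with start date or stop date on or after the first date of study drug dosing in MT-1186-A02", so use begun earlier and continued would qualify too.
- Protocol 8.1: "The use of AMX0035 will be allowed for patients in the event that it becomes commercially available via prescription in their respective country".
- SAP 3.2.1 makes additional AMX0035 treatment an intercurrent event, and SAP 9.1.4 tabulates "The number (%) of subjects with ICE1 of Additional/new AMX0035 treatment occurred during MT-1186-A02 and MT-1186-A04".
- SAP 8.3.1.2.2 nevertheless lists concomitant use with the ALS history items, beside a separate item, "Previous use of AMX0035".

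**The concern.** Both endpoints start at A02 randomisation, but most subjects can become Present only later. A fixed covariate credits a user's whole follow-up to Present, including the time before AMX0035 was started. Subjects who die early stay Absent because they had no chance to start. This is immortal-time bias in the Present v Absent contrast, which the model estimates as the subgroup main effect.

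The treatment comparison within each level also conditions on something that happened after randomisation. It is no longer protected by randomisation, and if the regimen or prognosis affects who starts AMX0035, each level's hazard ratio moves away from the randomised effect. Readers of a forest plot will take the row as a baseline subgroup like its neighbours. Elsewhere the plan recognises the problem: Protocol 17.4.5.3 uses inverse probability of censoring weights for the secondary estimand because starting AMX0035 is non-random.

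**Working it through.** **Who can become Present after an event.** Death rules out a later start. Protocol 9.6 makes tracheostomy and permanent ventilation withdrawal criteria, and concomitant medication is recorded only during participation, so for the secondary endpoint a recorded start after the event is largely excluded. A 12-point ALSFRS-R fall is not on the 9.6 list, and Protocol 11.3 sets no ALSFRS-R limit on AMX0035. Some of these subjects will stay and start later; others may leave under the investigator-judged exacerbation criterion. The share who can start after a primary event is therefore unknown and was varied.

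**Event rate, checked against the plan's power.** Protocol 17.2 gives 190 per group, hazard ratio 0.775, 65% control event-free at Week 48, two-sided alpha 0.20 and 96 weeks in total.

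- Control event-free at Week 96: 0.65² = 0.4225. Daily: 0.4225^0.775 = 0.513.
- Events: 190 × (0.5775 + 0.487) = 202.3.
- Power: Φ(√202.3 × |ln 0.775| / 2 − 1.2816) = Φ(0.531) = 70.2%, against the stated 70%.

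The exponential rate λ = −ln(0.65)/48 per week therefore matches the plan.

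**Simulation for the primary endpoint.** The true AMX0035 hazard ratio is 1. The Cox models contain treatment and ever-use, without and with their interaction. The documents give no uptake or start times, so these are assumptions.

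- Set-up A: 190 per group, 96 weeks of follow-up, 25% or 50% would-be starters, starts uniform over Weeks 0-96, 600 replicates per setting.
- Set-up B: 384 subjects with 202 followed to Week 96 (the counts in SAP 4.2), 20% to 60% would-be starters, starts uniform over Weeks 24-96, 150 to 400 replicates per setting.

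| Able to start after a primary event | Present v Absent HR, set-up A (25% / 50%) | Set-up B (20%-60%) |
|---|---|---|
| None | 0.43 / 0.35 | 0.22-0.29 |
| Half | 0.72 / 0.64 | 0.56-0.69 |
| All | about 1.0 | 0.93-1.01 |

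With set-up A, 50% would-be starters, starts confined to Weeks 48-96 and none after the event, the ratio is about 0.15.

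**The outputs that 9.4 specifies.**

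- Equal uptake, set-up A, true treatment HR 0.775: Absent 0.76-0.80, Present 0.76-0.78. The interaction test rejects in 2.7% to 5.8% of runs at a nominal 5%. In one further run with varying prognosis (log-hazard SD 0.8), both levels gave 0.82, so they did not diverge.
- Uptake 10 points higher on daily dosing, set-up B: Absent 0.81-0.86 with no starts after the event, 0.79-0.85 if half can, and 0.73-0.77 if all can.
- Uptake 30% v 60%, set-up B: Absent 0.96-0.98 with no starts after the event, and 0.88-0.89 if half can.

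The Absent ratio rises because higher uptake on daily dosing moves event-free daily subjects out of Absent and leaves that arm richer in events. No run tied uptake to prognosis, and the death/tracheostomy/ventilation endpoint was not simulated because the documents give no event rate for it.

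**The case against.** A reader might infer that Present requires event-free survival on the primary endpoint, and so that AMX0035 must look strongly protective. The documents do not support that: a 12-point fall does not force withdrawal, and ratios of 0.2-0.3 are only the extreme case with no later starts. A reader might also infer that the planned interaction test is invalid. With equal uptake it is not inflated. Section 9.4 calls for treatment effects by subgroup and interaction p-values; it does not ask for a Present v Absent ratio.

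The drift in the Absent treatment effect needs an imbalance in uptake that nothing in the documents predicts for a double-blind comparison. Its size at 10 points is well inside sampling error: with a standard error of about 0.165 on the log scale, 0.775 × exp(±1.96 × 0.165) runs from 0.56 to 1.07. AMX0035 is also handled in both estimands and its use is tabulated by arm. This is one row of fifteen, without type I error control (SAP 7.2), in a study already being terminated (SAP 5.1 and 5.2).

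All of that limits the weight of the point. It does not make the factor a baseline one. Equal uptake cannot be presumed if the regimens differ in efficacy, and the text gives no safeguard if they do.

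**Conclusion.** The point holds in this limited form. Following SAP 9.4 as written conditions on AMX0035 use that is largely post-randomisation and treats it as fixed from time zero. The certain defect is in the Present v Absent contrast. Its size on the primary endpoint depends on start times and on how many subjects start after a 12-point fall, and ranges from negligible to severe. For death, tracheostomy or permanent ventilation, later starts are largely excluded, so the bias runs the same way, but its size was not computed. The subgroup treatment effects are not randomised comparisons. They are near the truth under equal uptake and move towards 1 in Absent if uptake is higher on daily dosing. The qualifier *largely* matters, because use already under way at first dose and continued also counts as Present. All sizes rest on assumed uptake, start times and exponential events. The row should be changed, but the primary result does not depend on it.

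**What to change.** Remove concomitant AMX0035 use from the fixed-subgroup Cox models and the forest plot in SAP 9.4. If its role is of interest, choose one of these and state it before unblinding or, failing that, label it post hoc:

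- a time-dependent covariate that switches on at the AMX0035 start date, with its treatment interaction;
- a landmark analysis that classifies use at a fixed week among subjects still at risk.

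Either should be described as non-randomised. A subgroup on AMX0035 use at A02 baseline is an option only if enough subjects were using it then. The existing previous-use item is not a ready replacement: the SAP gives no derivation for it, the only prior-medication rule in 8.3.1.3 requires a stop date before first dosing, and the row could be nearly empty.

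The cost is a short SAP edit to drop the row, plus modest programming for either model. AMX0035 use is already recorded in the CRF (Protocol 11.1 and 11.3), and the weighted analysis in Protocol 17.4.5.3 needs the start dates anyway.

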10. DATA PRESENTATION CONVENTIONS

10.1. Number of Digits to Report

Statistic	Specification	Apply to
Minimum, Maximum	Same number of DPs as the data captured in the datasets	All original (i.e. non-derived)
	see section 8.3	All derived data
Mean, Median, SD, SE, Confidence intervals	One more DP than used for Min Max	All
Percentages*1	1 DP	All
Ratios	3 DPs	All
p-values*2	3 DPs	All

^{*1} Percentages: use 1 place after the decimal point, except for the following cases: If the percentage is equal to 0, then then use "(0)" without a decimal

If the percentage is equal to 100, then use "(100)" without a decimal

If the p-value is less than 0.001, then use p<0.001

10.2. Treatments to Report

Treatment	For TFLs
Oral edaravone 105 mg administered	Edaravone 105 mg Once Daily
once daily	
Oral edaravone 105 mg oral dose,	Edaravone 105 mg On/Off
administered for 10 days followed by	
18 days of matching placebo for 12	
treatment cycles (on/off) for a total of	
48 weeks	

^{*2} p-values: use 3 places beyond the decimal point, except for the following cases:

Mitsubishi Tanabe Pharma America, Inc.

10.3. Analysis Visits to Report

Efficacy:

Analysis Visit	Apply to		
Parameter	CAFS	ALSFRS-R	%SVC
	ÅLSAQ-40		Body Weight
Screening		X	X
Baseline (A02 Day 1)		X	X
Week 4 (A02)		X	X
Week 8 (A02)		X	X
Week 12 (A02)		X	X
Week 24 (A02)	X	X	X
Week 36 (A02)		X	X
Week 48 (A02 and A04	X	X	X
Day 1)			
Week 60 (A04 Week 12)		X	
Week 72 (A04 Week 24)	X	X	X
Week 84 (A04 Week 36)		X	
Week 96 (A04 Week 48)	X	X	X

Safety:

Analysis Visit	Apply to			
	Laboratory Tests	Vital Signs	12-Lead ECGs	C-SSRS
Screening	X	X	X	X
Baseline (A02	X	X	X	X
Day 1)				
Day 8 (A02)	X (only for Japan)			
Week 2 (A02)				
Week 4 (A02)	X	X		X
Week 8 (A02)	X	X	_	
Week 12 (A02)	X	X		X
Week 16 (A02)				
Week 20 (A02)				
Week 24 (A02)	X	X	X	X
Week 36 (A02)	X	X		
Week 48 (A02	X	X	X	X
and A04 Day 1)				
Week 72 (A04)	X	X	X	X
Week 96 (A04)	X	X	X	X

Mitsubishi Tanabe Pharma America, Inc.

11. CHANGE FROM THE PROTOCOL

The FAS flag definition will be changed from "all randomized subjects who received at least 1 dose of study medication and had any efficacy data collected after randomization" to "all randomized subjects who received at least 1 dose of study medication" because all randomized subjects who randomized and received at least 1 dose of study medication should be analyzed regardless of post baseline efficacy data in order to estimate treatment effect properly.

12. SOFTWARE

All statistical analyses will be performed using SAS version 9.4 or higher.

